- Study population = 30 patients with autoimmune thyroid conditions referred to the University of Wisconsin endocrine surgery clinic for surgical management. Patients will be invited to join the study after the decision has been made to proceed with thyroidectomy as the clinical treatment of their autoimmune thyroid disease. Once they have decided to proceed with surgery, we will describe the study rationale and the risks and benefits to enrolling. We will explain that patients will be randomized to take steroids for 1 week prior to surgery, in addition to other medications that we give all patients before surgery. If they choose not to enroll in the study, their thyroidectomy will proceed as planned. For the study, 15 patients will be treated with steroids for 1 week prior to surgery, 15 will not receive steroids. Both otherwise receive the current standard of preoperative care. We are doing a stratified randomization in blocks of four within four groups of patients, as determined by category of diagnosis (Graves' vs. Hashimoto's) and BMI (<35 vs >=35). The small block size will allow for equal numbers of control and treatment subjects even if category sizes are small.
 - Inclusion Criteria: Graves' disease or Hashimoto's disease with positive thyroid autoantibodies (Thyroglobulin Antibody [TgAb], Thyroid peroxidase antibody [TPO], Thyroid Stimulating Ig antibody [TSI], and/or Thyrotropin Receptor antibody [TRAb]). This information is found in the patient's medical record which is available at the time of surgical consultation. If a patient has not had antibody levels checked prior (this is rare), we can discuss the trial with the patient and draw the first set of clinical and research labs. If the clinical labs return that antibody levels are negative, we will inform the patient that they are not eligible to participate and will withdraw them from the study and discard the

research serum sample. All patients must first agree to undergo total thyroidectomy for their disease before they are even approached about the trial.

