- Exclusion Criteria: Pediatric patients < 18. Prior treatment with radioactive iodine (RAI). Known diagnosis of thyroid cancer. Diabetic patients. Patients on any immunosuppressive regimen (such as organ transplant patients or patients treated for other autoimmune condition). Pregnant patients. Patients being treated for active infection. Any patient for whom the surgeon feels steroids would provide a clear benefit (ie. Extremely high auto-antibody levels with a very large, inflamed thyroid gland) will be treated according to the clinical judgement of the surgeon. If a surgeon feels steroids are indicated and prescribes them, the patient will not be eligible for the trial.
- Subject identification and recruitment. We will identify patients from our own clinic who have been referred to us for consideration of thyroidectomy as treatment for their autoimmune thyroid disease. Each surgeon spends time prior to each clinic looking through their patient list, and will flag anyone with an autoimmune thyroid disease coming to discuss thyroidectomy as a potential study participant. After the normal clinical consult, those patients who choose to undergo thyroidectomy and otherwise meet criteria will be given the opportunity to participate in the trial. This will all occur in the same physical setting of our UW endocrine surgery clinic.
- Because this is a small pilot study done with limited resources and designed for feasibility and generating preliminary data, patients and surgeons will not be blinded to treatment. The operating surgeon is typically the provider who does the preoperative assessment and provides medications and instructions directly to the patient, and we lack the resources to coordinate a study-specific preoperative visit.
 - Because participants are not blinded, knowledge of their group assignment may affect their behavior. Subject non-blinding should not affect our primary outcomes of thyroid difficulty, serum antibody, or cytokine levels. It may alter their responses on the QoL surveys, however, as steroids can cause a euphoric effect while a person is taking them. QoL surveys are to be administered before the study begins, and then not again until 6 weeks and 6 months after surgery when subjects are no longer taking the steroids, so the effect will be minimal. For secondary outcomes, subject non-blinding should not affect ultrasound measurements or surgical outcomes.

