 - Because surgeons are not blinded, it is possible that their responses for the thyroid difficulty scale will be altered by their knowledge of whether the subject took steroids. The logistics of having the patients leave the surgeons clinic not knowing their group assignment, then having a different researcher assign and provide the medication would be beyond the budget and capabilities of our team for this feasibility trial. We feel the benefits of ease of enrollment and ability to recruit sufficient patients outweigh the possible bias in the thyroid difficulty scale.
- There are no additional collaborating sites – this will all be performed at UW Hospitals and Clinics
- Identify information extracted from medical records – demographics, length of time of disease, lab values related to thyroiditis disease, indications for surgery,

surgical data including blood loss and length of operation, postoperative laboratory values related to thyroiditis.

- We know that glucocorticoids may decrease Immunoglobulin (Ig)G and IgA levels with moderate-to-high dose steroids given over short term. (10-20 percent at one week in rheumatoid arthritis patients)¹³, therefore we intend to collect serum for antibody levels at intervals more frequent than our standard of care.
- **Specimen/data collection, handling, storage**
 - Data will be collected electronically (REDCap) on the Institute for Clinical and Translational Research (ICTR) secure version of the software and on paper. The only data recorded on paper will be the Thyroid difficulty scale and the prednisone compliance survey and these will be stored in the PI's office in a locked file cabinet.
 - All information obtained and associated data files will be confidential and will be kept in a locked file or password protected secure departmental server through the department of surgery (U:). This server is backed up according to standard protocols. All computers used to access this server are password protected. The risk of breach of confidentiality regarding participation in the study outside of the scope of the research will be handled by carefully controlling access to study data only to personnel on the research team.

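### The protocol describes no allocation concealment for an open-label trial with one stated block size, and one sentence on survey timing lets the baseline quality-of-life score follow disclosure of the arm

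*Combined protocol and SAP*

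**What the plan says.** **Assignment.** Research Design and Methods plans 30 patients, 15 per arm, and says "We are doing a stratified randomization in blocks of four within four groups of patients". The strata are Graves' or Hashimoto's disease crossed with BMI below 35 or 35 and above. The reason given is balance: "The small block size will allow for equal numbers of control and treatment subjects even if category sizes are small".

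**Who does what.** Neither patients nor surgeons are blinded. "The operating surgeon is typically the provider who does the preoperative assessment and provides medications and instructions directly to the patient". The Data and Safety Monitoring Plan refers to the enrolling surgeon. The exclusion criteria add a judgement by that surgeon: "If a surgeon feels steroids are indicated and prescribes them, the patient will not be eligible for the trial". Having the patient leave clinic unaware of the arm, "then having a different researcher assign and provide the medication would be beyond the budget and capabilities of our team", is ruled out.

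**Pending antibodies.** In the rare patient without an earlier antibody result, bloods are drawn after the trial is discussed. If they are negative, "we will inform the patient that they are not eligible to participate and will withdraw them from the study". The text does not say whether assignment waits for the result.

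**Baseline quality of life.** SF-12 and ThyPRO are listed as primary outcomes. The non-blinding paragraph accepts that answers may be altered, "as steroids can cause a euphoric effect while a person is taking them", but calls the effect minimal because "QoL surveys are to be administered before the study begins" and are repeated only at 6 weeks and 6 months after surgery. The schedule table puts the baseline at the preoperative clinic visit, 2 to 4 weeks before surgery. The Preoperative Testing paragraph of Study Procedures asks only that the online surveys be done at some point before the operation.

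**The concern.** Concealment and blinding are different safeguards. Blinding concerns what people know after assignment. Concealment concerns what the enrolling person knows before the patient is committed to the trial, and an open-label trial can have it. The protocol discusses the first at length and does not mention the second.

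The gap matters here because an exclusion rests on the surgeon's opinion that steroids are indicated. If the next arm were known or predictable, that opinion, or the decision to offer the trial, could depend on it, and the arms could then differ in gland size and inflammation before treatment. Those features plausibly drive the difficulty score, another primary outcome.

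The second issue is internal to the plan. Its argument that quality-of-life bias is minimal relies on no survey being answered on prednisone, and its procedures do not secure that. A baseline made to look better by the drug would make the steroid arm's later improvement look smaller.

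Statistical Considerations uses these data for the sample size of the definitive trial, so a distortion could carry forward.

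**Working it through.** The plan gives no figure for predictability or for the quality-of-life effect, so there is none to reproduce. Inputs from the documents are: block size 4, four strata, 30 patients, 15 per arm, preoperative visit 14 to 28 days before surgery, and prednisone on the 7 days before surgery.

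**1. One complete block of four.** There are 6 equally likely orders: AABB, ABAB, ABBA and their mirror images.
- Known in advance: the fourth place always (6 of 6), and the third when the first two match (2 of 6). Total (6 + 2)/(6 × 4) = 8/24 = 33%.
- Best guess, place by place: 1/2 + 2/3 + 2/3 + 1 = 17/6 correct per block, and (17/6)/4 = 71%. Chance is 50%.

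**2. Thirty patients in four strata.** Last blocks are usually incomplete, so this was simulated. Stratum shares are not in the documents. Four assumed mixes were used, from 25/25/25/25 to 60/20/15/5. The observer knows the possible block sizes and all earlier assignments in the stratum, and guesses optimally.

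| Block sizes | Known in advance | Guessed correctly | Arms within 2 | Exactly 15/15 |
|---|---|---|---|---|
| 4 only | 28% (about 8 of 30) | 68% | 91–92% | 43% |
| 2 and 4 mixed | 9% | 70% | 94% | 46% |
| 4 and 6 mixed | about 6% | 66–67% | about 88% | 39% |

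Results barely change across the assumed mixes. Varying the block size removes most of the certainty but hardly affects guessing, and mixing 2 and 4 raises it slightly. Hiding the list stops direct sight of the next arm, but an observer who sees all past arms would keep the 28% and 68%. The main protection is therefore to fix the eligibility judgement before release.

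**3. Survey timing.** The first dose is 7 days before surgery, so the preoperative visit falls 14 − 7 = 7 to 28 − 7 = 21 days before it. A survey completed at that visit is off drug and satisfies the non-blinding paragraph, the schedule table and Study Procedures together. A survey completed online in the last week satisfies only Study Procedures.

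**4. Size of the quality-of-life effect (illustration, inputs assumed).** Suppose 1 to 5 of the 15 steroid patients answer on prednisone and their scores shift by 0.2 to 0.5 SD. The contrast in change from baseline moves by (1/15) × 0.2 = 0.01 SD to (5/15) × 0.5 = 0.17 SD. If the SD of change equals the SD of a single score (correlation 0.5, assumed), the standard error of the contrast is √(1/15 + 1/15) = √(2/15) = 0.37 SD. Any effect of merely knowing the arm is not in this figure.

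**The case against.** **The plan is silent, not open.** A reader might infer that nothing conceals the next assignment. The documents do not show that: they do not say the list is visible to anyone. They say that the operating surgeon typically, not always, assesses the patient and provides medication. Disclosure of the arm at the clinic visit is implied by the paragraph on logistics but not stated. This objection stands, and the claim is limited to what is described.

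**The 28% and 68% describe an observer who does not appear in the documents.** This also stands. They are ceilings on predictability, not estimates of bias, and no figure is offered for a surgeon who sees only his or her own patients.

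**Non-blinding was accepted openly on budget grounds.** This does not answer the point. The accepted bias is in responses after assignment; foreknowledge before enrolment is not discussed.

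**Eligibility already precedes the offer, and analysis is by initial group.** A reader might infer that patients can be excluded on the steroid criterion after assignment. The text does not say so, and the intent-to-treat rule points the other way. But prior eligibility does not protect if the next arm is already known, and nothing requires the judgement to be recorded before assignment.

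**The survey passages do not conflict.** Correct: one survey at the preoperative visit satisfies all three. The fault is that the procedural sentence is looser than the bias argument needs.

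**This is a feasibility pilot.** That limits the consequence. The plan also does not say whether the effect estimate or only the variance will feed the later sample size, so harm to the definitive trial is possible but not shown.

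**Conclusion.** The point holds as a gap in described safeguards. The protocol combines one stated block size, visible strata, open treatment and an enrolling surgeon with a subjective exclusion, and it describes no concealment and no recorded order of judgement and assignment. The ceiling on predictability is about 28% known and 68% guessed, on the assumption of full knowledge of earlier arms in each stratum. The documents do not support saying that the list is open or that any surgeon could predict assignments to that extent.

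The survey point is smaller. Study Procedures permits a baseline that the protocol's own bias argument assumes will not occur. On assumed inputs the shift is 0.01 to 0.17 SD against a standard error of about 0.37 SD. A reader might infer that the quality-of-life comparison is seriously biased, and these figures do not support that.

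Both parts should be changed because the remedy is cheap. Confidence is medium, since the actual mechanism may be sound but unwritten.

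**What to change.** 1. **Conceal and sequence.** State that the allocation list is hidden from enrolling surgeons, for example a REDCap list loaded by the biostatistics team. Release each assignment only after consent and a time-stamped eligibility record that includes the surgeon's steroid judgement and the positive antibody result. This also makes plain that the steroid exclusion applies before assignment.
2. **Align the survey wording.** Amend Study Procedures to match the non-blinding paragraph and the schedule table: SF-12 and ThyPRO are completed at the preoperative visit before the arm is disclosed, and the completion time is recorded. Flag later baselines rather than blocking assignment. A hard gate would make baseline response 100% among randomised patients by construction, and questionnaire response is a feasibility aim.
3. **Optional.** Vary block size at random and keep the sizes out of the protocol given to surgeons. Mixing 2 and 4 keeps the balance aim and cuts certainty to 9%. Mixing 4 and 6 cuts it to about 6% but lowers the chance of arms within 2 from 91–92% to about 88%. Guessing stays at 66–70% either way.

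**Cost.** Protocol wording and one list, with no extra visit and no second researcher. The documents name REDCap only for data capture and the biostatistics core for analysis, so their capacity to run allocation should be confirmed. Two surveys of 10 to 20 minutes each, 20 to 40 minutes already required, move ahead of disclosure and may slightly lower enrolment; refusals for this reason should be counted. The rare patient with antibodies pending is assigned after leaving clinic.

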 - Concomitant medications allowed/disallowed: No other steroids or immunosuppressive medications, No antibiotics, antitubercular drugs, or anti-fungals. No anticoagulants. Caution in many anti-seizure medications.
 - No placebo
 - While chronic systemic steroids may impair wound healing, there is literature to support that acute (< 10 days), high-dose systemic corticosteroid use has no clinically significant effect on wound healing¹⁴
 - The prednisone dose is within the accepted guidelines for rapid prep for Graves’ disease patients, and is considered a moderate dose. It is expected to contribute negligible increased risk for wound complications in this population where wound infection rates are already extremely low (less than 0.5%).
- **Data and Safety Monitoring Plan:**
 - This is a study that involves randomizing patients to receive a prescription drug, therefore is greater than a minimal risk study. It is using a commonly prescribed medication for a short duration and has been shown to have a low incidence of adverse events at these doses and durations. Prednisone is already prescribed

in a subset of similar patients to our population outside the context of a trial (Graves' disease requiring rapid surgical prep). Potential problems will be monitored and handled by the primary surgeon, clinic staff and principal investigator. This is appropriate given the small number of participants (15 subjects will receive the intervention drug), single site, and low risk medication. We will not assemble a formal *external* Data and Safety monitoring committee..

- [name] will be notified by the enrolling surgeon each time a subject enrolls in the trial and of any protocol deviations. Adverse events from the study medication will be reported immediately. We anticipate that the manner in which subjects will report adverse events is by (1) directly notifying the principal investigator as directed in the informed consent document, (2) calling our clinic staff who will notify [name], or (3) by reporting side effects and amount of drug taken on the drug compliance survey on the day of surgery.
- Protocol violations and deviations, side effects, and adverse events will be noted in the secure RedCap database.
- A monthly clinical research meeting occurs among our group to discuss all clinical research, and this study will become a standing item on our agenda during the duration of the trial for any surgeon to discuss possible adverse events or concerns

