- Given low rates of wound infection in this population, any wound infection requiring treatment with antibiotics in the steroid group will be considered an adverse event (AE) and will be investigated immediately by the principal investigator and operating surgeon, and reported to the IRB within 14 business days. If a wound infection requires an operation, it is considered a serious adverse event (SAE), although it is not immediately life threatening or debilitating to other subjects, so also will be reported with 14 business days to the IRB. If a second wound infection requiring antibiotics or surgery occurs in the steroid treated group, enrollment will immediately cease and it will be reported as a SAE in the same 14 day timeframe, when we will closely scrutinize these cases with the help of the IRB to determine whether it is safe to proceed. Monitoring for wound infections will occur in the context of our usual clinical care. We will see every wound in person at the postoperative visit, but otherwise we rely on patients self-reporting to alert clinic staff if they have concerns (redness, warmth, drainage) about their incisions. No specific study-specific instructions will be given to study subjects, we will simply ask them to call the clinic staff if they have any concerns, and clinic staff will be trained to immediately notify [name] if a study patient reports wound complications.
- Statistical Considerations: Provides an explanation as to why the number of subjects was chosen and the means for analyzing data will meet the specific aims/study objectives
 - As a small pilot, feasibility study, the size of 30 is based on our estimate of a realistic recruitment rate for the future definitive trial. We see approximately 70 potential subjects in our clinics per year, and our listed exclusion criteria are rare in our population. We estimate that fewer than one fourth will not meet criteria, and an additional one fourth may decline to participate. From the patient perspective, enrollment involves only answering QoL surveys and possibly taking a medication 1 week prior to surgery, the risks and effort are not much greater, which is why we estimate a generous rate of inclusion. We are giving ourselves 1 year to enroll all 30 patients (with an additional 6 months to collect follow up data). Our biostatistics team has already been engaged and feels this is an aggressive but realistic expectation. For all primary aims, data will be analyzed

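### Fixed blocks of four, printed in the protocol of an open single-site trial with no described concealment, make about 28% of allocations certain to anyone who knows the earlier ones in that stratum; 15:15 is a target, not a guaranteed split

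*Combined protocol and SAP*

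**What the plan says.** Under Research Design and Methods, the study population item gives the size ("Study population = 30 patients with autoimmune thyroid conditions"), the arm sizes ("15 patients will be treated with steroids for 1 week prior to surgery, 15 will not receive steroids") and the scheme: "We are doing a stratified randomization in blocks of four within four groups of patients", the groups being Graves' or Hashimoto's crossed with BMI below 35 or at least 35. It adds that "The small block size will allow for equal numbers of control and treatment subjects even if category sizes are small". The Data and Safety Monitoring Plan repeats that "15 subjects will receive the intervention drug".

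Other parts of the protocol bear on who could know the allocations:

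- Patients and surgeons are not blinded. The operating surgeon typically does the preoperative assessment and hands over medication and instructions. Having another researcher make the assignment is ruled out on budget.
- Exclusion Criteria let a surgeon who sees a clear benefit from steroids prescribe them, which takes the patient out of the trial.
- There is one site. The enrolling surgeon reports each enrolment to the principal investigator, and the trial is a standing item at the group's monthly research meeting (Data and Safety Monitoring Plan).

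The documents do not say who generates or holds the list, when an assignment is released, or what happens to incomplete blocks. They give no expected stratum sizes.

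**The concern.** Permuted blocks buy balance at the price of predictability. With one known block size and open treatment, the end of each block can be read off from its beginning. Here the person who decides whether to offer the trial, and who may instead prescribe steroids outside it, also learns the assignments. If the next assignment can be foreseen, the choice of whom to enrol can depend on it, knowingly or not.

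The Thyroid Difficulty Scale, listed as a primary outcome, is rated by the surgeon and depends on the gland. If patients with large, inflamed glands were enrolled or diverted according to the expected arm, the arms would differ before treatment. The pilot's estimate of willingness to enrol would be affected too. The protocol discusses bias from non-blinding at some length, but not selection at entry, which is a separate matter and can be prevented without blinding.

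A lesser point is that the text presents 15:15 as settled, although the scheme does not guarantee it.

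**Working it through.** **Inputs.** From Research Design and Methods: N = 30, four strata, blocks of four (taken as 2:2). Stratum shares are not given. Where needed they are assumed: Graves' share 30–90% and BMI ≥35 share 5–50%, independent. The predictability simulations use four mixes (equal; 45/25/20/10; 35/15/35/15; 60/15/20/5).

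**1. The plan's own figure.** 30 × 1/2 = 15 expected per arm. As an expectation it reproduces.

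**2. Certain allocations in one full block of four.** The fourth is always certain. The third is certain if the first two agree, with probability 1/3. Expected number: 1 + 1/3 = 4/3, or 33.3% of the block. An incomplete block contributes 1/3 if it holds three patients, otherwise 0.

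**3. Over 30 patients.** Certain allocations = (full blocks × 4/3) + (strata with remainder 3) × 1/3.

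| Stratum sizes | Full blocks | Certain | Share of 30 |
|---|---|---|---|
| 16/4/8/2 | 7 | 9.33 | 31.1% |
| 8/8/7/7 | 6 | 8 + 0.67 = 8.67 | 28.9% |
| 10/5/10/5 | 6 | 8.00 | 26.7% |
| 14/6/7/3 | 5 | 6.67 + 0.67 = 7.33 | 24.4% |

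Remainders can only sum to 2, 6 or 10, and going through all of them shows that 24.4% and 31.1% are the extremes. Simulation over the four mixes averages about 28%.

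**4. Blocks of 2 and 4 in random order, equally likely.** Mean block length is 3. Certainty arises only when a block of four opens with two alike (probability 1/2 × 1/3 = 1/6 per block).

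- Counting only the allocation that follows directly: (1/6)/3 = 5.6% in complete blocks, about 5% once incomplete blocks are allowed for.
- Counting the fourth allocation too, as step 2 does: (2/6)/3 = 11.1% in complete blocks, about 9% in simulation over the four mixes. This is the like-for-like comparison with 28%.

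Both counts assume an observer who knows that the sizes are 2 and 4.

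**5. Guessing the arm that is behind.**

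- Fixed fours: (1/2 + 2/3 + 2/3 + 1)/4 = 70.8% correct in complete blocks.
- Mixed: a block of two gives 1/2 + 1 = 1.5 correct and a block of four gives 2.833, so (1.5 + 2.833)/2 ÷ 3 = 72.2%.
- With 30 patients in four strata, the figures are about 68% and 70%.

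**6. Arm sizes with fixed fours.** Only the last, incomplete block of a stratum can be unbalanced. A remainder of 1 or 3 gives a difference of ±1. A remainder of 2 gives 0 with probability 2/3 and ±2 with probability 1/6 each. Since 30 is not a multiple of four, at least one block stays incomplete. Four remainders of 2 would need a total divisible by four, so the largest overall difference is 6 (18:12).

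- Fixed sizes 16/4/8/2: P(15:15) = 2/3 = 66.7%.
- Fixed sizes 10/5/10/5: 0.5 × 0.5 + 2 × 0.2222 × 0.25 = 36.1%.
- Four equal shares, averaged over stratum sizes: 15:15 in 43.2%, 16:14 in 48.5%, 17:13 in 8.0%, 18:12 in 0.3%.
- Over the assumed grid: 15:15 in 42.8–48.4%, 16:14 or closer in at least 91%, 17:13 or closer in at least 99.6%.
- BMI ≥35 share of 1–2%: 15:15 in 52–56%. If those strata are empty: 58.3%.
- Mixed blocks of 2 and 4: 15:15 in about 46–47%, against 42–44% for fixed fours simulated under assumed mixes.

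**7. Cost of imbalance.** Variance relative to 15:15 at 18:12 is (1/18 + 1/12)/(2/15) = 1.042. At 17:13 it is 1.018 and at 16:14 it is 1.004.

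**The case against.** On predictability, the best defence is that 28% applies to someone who knows every earlier allocation in the stratum. Several surgeons enrol, each from their own clinic, and the documents do not say that they share assignments or see the list. That stands: the opportunity is conditional, and a reader should not infer that surgeons will in fact foresee allocations. But nothing in the documents closes the route, and open treatment, one site and a standing meeting item make shared knowledge plausible.

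It is also fair that varying the block size is not a clean gain. Blocks of two are easy to guess, so an informed guesser does slightly better (about 70% against 68%). Concealment is therefore the essential part.

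On arm sizes, three stronger readings are tempting and fail:

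- *That the sentence on small categories has the method backwards.* It does not. Small blocks balance better: exact 15:15 occurs in roughly 43–45% of trials with fours, 37% with sixes and 31–36% with eights under assumed mixes, and in 14.4% with simple randomization. The wording claims that equality is allowed for, not guaranteed.
- *That an exact split fails in most trials.* This depends on stratum shares that the documents do not give, and the probability passes one half when some strata are nearly empty.
- *That the safety plan and the comparisons depend on 15.* The safety plan cites the number only as one sign that the trial is small, the enrolment halt is triggered by a count of infections, and the planned mixed model and t-tests do not need equal arms. Under Statistical Considerations, "the size of 30 is based on our estimate of a realistic recruitment rate for the future definitive trial".

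**Conclusion.** The point holds as a low-cost improvement, not as a flaw that undermines the pilot. Fixed blocks of four make 24% to 31% of allocations (about 28% on average) certain to an observer who knows the block size and the earlier allocations in that stratum. This range needs no assumption about stratum shares. Whether any surgeon would be such an observer is not stated, so the size and direction of any selection bias cannot be calculated.

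The arm-size point is one of wording. Fifteen per arm is the expected split but is not guaranteed. Exact 15:15 has a probability of about 43–48% over the assumed shares and 36–67% for particular fixed stratum sizes. The statistical cost is negligible: at most 4.2% in variance, and under 2% in more than 99.6% of trials over the assumed grid.

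**What to change.** - Hold the stratified list where enrolling surgeons cannot see it. REDCap, already used for data capture, is an obvious place if its set-up at the site permits. This is the essential step.
- Release each assignment only after consent and confirmed eligibility are recorded, including any surgeon's decision to treat outside the trial.
- Generate the list with randomly varying block sizes and keep those sizes out of the protocol text available to surgeons. With sizes 2 and 4, certain allocations fall from about 28% to about 5–9% and exact balance improves slightly, in return for a small rise in guessability if earlier allocations become known.
- State a target of 15 per arm, about 15 expected, with a range that matches the list adopted. For fixed fours that is 12 to 18. For mixed 2s and 4s, each of four strata can end two apart, so 11 to 19 is possible though very rare.
- Soften the sentence on equal numbers in small categories: the blocks limit imbalance but do not remove it.

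The cost is a different list setting and a few lines of text. No extra patients or visits are needed, and because concealment does not require blinding, the protocol's resource argument against blinding does not stand in the way.
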